7. TRIAL DESIGN

A single-blind, randomised, phase II multi-centre study to determine the reactogenicity and immunogenicity of heterologous boost COVID-19 vaccine schedules.

7.1. Setting

Multicentre study conducted through academic and NHS clinical trials sites.

7.2. Trial duration

Total duration of each participant will be approximately 26 weeks (for those primed in the community) or 34 weeks (those primed in the study). The total trial period will be approximately 10 months.

7.3. Study groups

A total of up to 270 (+ up to an additional 10%) participants will be enrolled and randomised (1:1:1) as below:

Group	Arm	Prime (Day 0)	Boost (day 56)
	1	BNT162b2	BNT162b2
	2	BNT162b2	BNT162b2 (one-third dose)
	3	BNT 162b2	NVXCov2373

After 29th November 2021, the enrolment of participants who have received their first dose of COVID-19 vaccine in the community will be temporarily suspended. Only participants who have received their first dose of COVID-19 vaccine in the study will be randomised to a second dose. They will be randomised (1:1) as below:

Group	Arm	Prime (Day 0)	Boost (day 56)
	1	BNT162b2	BNT162b2
	2	BNT162b2	BNT162b2 (one-third dose)

Randomisation will be performed at the time of the second dose, and stratified by study site and anti-nucleocapsid IgG status at baseline where available.

The study will be single-blind, i.e. while staff involved in study delivery will be aware of what vaccine schedule the participant is receiving, the participant themselves will remain blinded to their boost vaccine. This blind will be maintained by applying a masking tape over the vaccine syringe as detailed in the study clinical study plan. Laboratory staff will also be blinded to the vaccine schedule received.

7.4. Participants testing COVID-19 positive

Participants who acquire new infection with SARS-CoV-2 (as determined by SARS-CoV-2 antigen or PCR tests) will be asked to record this in their electronic/paper diary, and may continue in the study.

The UKHSA recently recommended increasing the interval between COVID-19 infection and vaccination from 4 weeks to 12 weeks in healthy 12 to 17 year olds. This is in part because young people are likely to have high levels of protection for at least 3 months after COVID-19 infection, meaning an earlier vaccine boost might not be necessary. It is also possible, though not confirmed, that a longer interval between infection and vaccination might reduce further the very small existing risk of myocarditis. The recommendation adopts a highly precautionary approach. However, 12 to 17 year olds at “high risk” and all adults are still advised to wait 4 weeks between infection and vaccination. On the advice of our independent Trial Steering Committee, we will still be offering a second dose of vaccination from 4 weeks after the first positive COVID-19 test confirming infection. This is in line with the recommendation for ‘high-risk’ 12 to 17 year olds. This is to allow as many adolescents as possible to take part in this study, and to enable us to provide results as quickly as possible to the JCVI.

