Many young people in the UK have already been infected with COVID-19. It is important to understand the response to vaccination in this group. Therefore, participants enrolled in this study will include those with previous proven or suspected COVID-19.

Young people aged 12 to 17 years are now being invited to receive Pfizer-BioNTech vaccine, and many may have already received one dose by the time the study commences. Individuals who have received one dose of Pfizer-BoiNTech vaccine in the community will be eligible to enrol in the study at least 8 weeks after receiving their first dose.

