6. OBJECTIVES AND OUTCOME MEASURES

	Objectives	Outcome Measures	Timepoint(s)
Primary	To evaluate the reactogenicity of heterologous boost at least 8 weeks following BNT162B2 prime vaccine administered to adolescents.	Solicited reactions systemic	7 days after boost immunisation
Secondary	To assess safety of heterologous boost COVID-19 vaccines	Serious adverse events Adverse events of special interest	Throughout the study
	To characterise immunogenicity of heterologous & homologous boost schedules	Anti-spike immunoglobulins	D0*, 56, post prime D 14, 28, 132, 236 post boost
		Anti-nucleocapsid immunoglobulins	D0*, 56 post prime D132, 236 post boost
		Cellular immune responses by ELISpot	D0*, 56 post prime

			D 14, 132, 236 post boost
	To assess reactogenicity and safety of heterologous and homologous boost schedules of COVID-19 vaccines	Solicited local reactions	7 days after prime* and boost immunisation
		Unsolicited reactions	28 days after prime* and boost immunisation
	To evaluate immunogenicity, safety & reactogenicity of COVID-19 vaccines in participants seropositive for SARS-CoV-2 nucleocapsid IgG at enrolment, compared with seronegative	Immunogenicity, safety & reactogenicity endpoints as outlined above	Timepoints as outlined above
Exploratory	To assess incidence of SARS-CoV-2 infection in participants receiving heterologous & homologous prime/boost schedules	Self-reported SARS-CoV-2 infection, from community testing	Throughout the study
	To further characterise the blood antibody response	Neutralizing and Functional antibody assays	D0*, 56 post prime D 14, 28, 132, 236 post boost
	To characterise and compare the mucosal immune response to immunisation with homologous and heterologous COVID-19 vaccines using nasal fluid (collected using SAM-strips) and saliva samples	IgA & IgG ELISA and exploratory immunological assays	D0*, 56 post prime D14 post boost
	To determine normal ranges of markers of cardiac muscle damage in adolescents, and to assess change post-immunisation	High sensitivity troponin and N-terminal pro B-type natriuretic peptide (NT-proBNP)	D0*, 56 post prime D14, 28 post boost

* Only for participants receiving prime vaccination in the study

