12.2. Description of statistical methods

A fully detailed statistical analysis plan will be developed and signed by the chief investigator prior to any data analysis being conducted. In brief, the analysis will incorporate the following:

Safety and reactogenicity

All SAEs will be presented for each group using descriptive analyses. Counts and percentages of each local and systemic solicited adverse reaction from diary cards, and all unsolicited AEs, and AEs of special interest will be presented for each group. Comparisons between the arms will be made using Fisher's exact test.

Immunogenicity

Highly skewed ELISA data will be log-transformed prior to analysis. The geometric mean concentration (GMC) and associated 95% confidence interval (CI) will be summarised by computing the anti-log of the mean of the log-transformed data.

The GMRs and CIs post boost will be calculated for each of the heterologous arms when comparing to the homologous arm.

Spike-specific T cell responses (ELISPOT) will be presented as geometric means and confidence intervals, or medians and interquartile ranges if non-normally distributed after log-transformation.

Comparisons of continuous immunogenicity data between different arms or at different time points will be made using a t-test if normal distribution can be rendered after log-transformation. Otherwise, Mann Whitney U test will be used.

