23. APPENDIX A: SCHEDULE OF PROCEDURES

Study timeline	Screening	D0	D56	D14 post boost	D28 post boost	D132 post boost	D236 post boost
Study window		Within 120 days of screening	Day 56–70 post prime vaccine at D0 or Day 56 + post prime vaccination in community	Day 12-17 Post D56	Day 28-42 post D56	Day 112-152 post D56	Day 224-252 post D56
Pre - screening online consent	X*						
Informed consent	X	X					
Medical history	X	X					
Interim medical history		X	X	X	X	X	X
Physical examination (as required)	(X)	(X)	(X)	(X)	(X)	(X)	(X)
Urine test (Pregnancy) (if required)		(X)**	X				
COVID-19 vaccination		(X)**	X				

COVID-19 immunogenicity bloods		(X)**	X	X	X	X	X
Troponin and NT-proBNP blood test		(X)**	X	X	X		
Saliva and nasal fluid test (if participant consents)		(X)**	X	X			
Diary review			X	X	X		
SAE/AESI check			X	X	X	X	X

* Pre - screening online consent. Restricted to taking a limited medical history online, contacting the GP for further medical record if required and telephone screening visit(s)

**Procedures performed only if prime dose administered in the study

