25. APPENDIX C: BLOOD SAMPLING

Study timeline	D0	D56	D14 post boost	D28 post boost	D132 post boost	D236 post boost
COVID-19 vaccination	X	X				
Secondary endpoints	Anti-spike IgG* Anti-nucleocapsid IgG* ELIspot* Troponin & NT-proBNP*	Anti-spike IgG Anti-nucleocapsid IgG ELIspot Troponin & NT-proBNP	Anti-spike IgG ELIspot Troponin & NT-proBNP	Anti-spike IgG PBMC for storage Troponin & NT-proBNP	Anti-spike IgG Anti-nucleocapsid IgG ELIspot	Anti-spike IgG Anti-nucleocapsid IgG ELIspot
Total volume blood per visit	16	16	16	16	16	16
Total volume by end of study						96 ml

* Procedures performed only if prime dose administered in the study

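### With no anti-nucleocapsid test between the boost visit (D56) and D132 post boost, undiagnosed infections cannot be recognised in the D28 anti-spike comparison

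*Protocol*

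**What the plan says.** Infected participants stay in follow-up: section 7.4 says they "will be asked to record this in their electronic/paper diary, and may continue in the study". For immunogenicity, section 12.2 states: "The GMRs and CIs post boost will be calculated for each of the heterologous arms when comparing to the homologous arm".

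Sections 3 and 6 set anti-spike at D14, D28, D132 and D236 post boost. For anti-nucleocapsid the time points are "D0*, 56 post prime D132, 236 post boost", where the asterisk limits D0 to those primed in the study. Appendix C agrees. Its D14 cell reads "Anti-spike IgG ELIspot Troponin & NT-proBNP" and its D28 cell reads "Anti-spike IgG PBMC for storage Troponin & NT-proBNP"; neither lists anti-nucleocapsid. Appendix A gives the D132 window as "Day 112-152 post D56".

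Infection is otherwise recorded from community tests: diary entries (7.4 and 9.6.1.1.5), self-report as an exploratory outcome (section 6), and a positive validated test as an adverse event of special interest (11.10), which 11.6.2 requires sites to ask about at every visit. Appendix A schedules no study antigen or PCR test. The optional nasal fluid sample serves mucosal antibody work.

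**The concern.** The protocol expects infection to be common in this age group: "Many young people in the UK have already been infected with COVID-19. It is important to understand the response to vaccination in this group". Sections 10.1.1 and 10.1.2 describe both vaccines as spike-based. Anti-spike can therefore rise after either vaccination or infection, while anti-nucleocapsid points to infection. At D28 the trial has the first measurement without the second.

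The trial asks whether a one-third or heterologous boost gives a response close to that of the full dose. If infection brings participants in both arms to a similar antibody level, undetected infections pull the GMR towards 1, so a weaker schedule looks closer to the standard one than it is. An analysis plan can decide how to treat an infection that is known. It cannot supply a marker from an assay that was not scheduled.

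**Working it through.** **1. The schedule side by side** (sections 3 and 6, Appendices A and C)

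| Visit | Window after boost | Anti-spike | Anti-nucleocapsid |
|---|---|---|---|
| D56 (boost) | 0 | yes | yes |
| D14 post boost | 12–17 days | yes | no |
| D28 post boost | 28–42 days | yes | no |
| D132 post boost | 112–152 days | yes | yes |
| D236 post boost | 224–252 days | yes | yes |

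After the boost-day sample, serology is silent for 112 to 152 days.

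**2. Who is affected**

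- Positive community test: identified and dated from the diary or the visit check.
- No positive test, seronegative at D56 and at D132: can be cleared for D14 and D28, but only once D132 is available.
- No positive test, seronegative at D56, seropositive at D132: infected at an unknown time, which may fall before or after D28. This is the ambiguous group.
- Already seropositive at D56: seroconversion cannot show reinfection, whatever the schedule.

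**3. The protocol's own detectable GMRs** (section 12.1: 90% power, two-sided 0.05, 90 per arm)

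GMR = 10^[(1.960 + 1.282) × SD × √(2/90)]

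| log10 SD | Normal formula | t-based | Protocol |
|---|---|---|---|
| 0.4 | 1.561 | 1.564 | 1.57 |
| 0.5 | 1.744 | 1.750 | 1.75 |
| 0.6 | 1.950 | 1.957 | 1.96 |

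The figures reproduce. At SD 0.4 the counterpart below 1 is 0.64.

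**4. Effect of undetected infections on the D28 GMR**

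The protocol gives no attack rate and no fold rise after infection, so the following are assumptions. A share q of each arm has an undetected infection, and infected participants reach the same level in both arms. Then

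observed GMR = (true GMR)^(1−q)

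and, approximating the spread with one fold rise f for both arms,

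SD' = √[0.4² + q(1−q)(log10 f)²].

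True GMR 0.64, SD 0.4, 90 per arm, f from 2 to 5:

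| q | Observed GMR | SD' | Power |
|---|---|---|---|
| 0 | 0.640 | 0.400 | 90% |
| 2% | 0.64^0.98 = 0.646 | 0.402–0.412 | 89–87% |
| 5% | 0.64^0.95 = 0.654 | 0.405–0.428 | 86–82% |
| 10% | 0.64^0.90 = 0.669 | 0.410–0.452 | 81–74% |

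**5. Is 2–10% a reasonable range?** At an assumed 1–5% infected per week, the four-week risk is 1 − 0.99^4 = 3.9% to 1 − 0.95^4 = 18.5%. That counts all infections. If half go undiagnosed, again an assumption, q is about 2–9%.

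**6. Other models.** If infection multiplies titres by the same factor in both arms and the shares are equal, the GMR does not move; only the GMCs and the spread rise. If the shares differ by 5 points, the GMR is biased by a factor of 2^0.05 = 1.04 to 5^0.05 = 1.08.

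**The case against.** Most infections that matter may already be visible. Positive tests are recorded by several routes and are dated, and retrospective clearing at D132 will settle most of the rest. Section 9.7.1 also covers antibodies to non-spike antigens and lets investigators run further antibody assays, so D28 serum that remains could be tested under the present text. Immunogenicity is a secondary endpoint, and exposure before D14 is only 12 to 17 days. All of this stands and limits the point. It does not remove it: permission to run an assay is not a schedule, and retrospective clearing leaves the undiagnosed seroconverters undated.

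Three stronger readings are tempting, and the documents do not support them.

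- A reader might infer that infected participants remain in the GMC and GMR analyses. Section 7.4 speaks of continuing in the study, not of the analysis set, and section 12.2 defers detail: "A fully detailed statistical analysis plan will be developed and signed by the chief investigator prior to any data analysis being conducted". That plan is not at hand, so the lack of a rule in the protocol is no finding.
- A reader might infer that infection can never be separated from vaccine response or dated. That is true only of undiagnosed infections.
- A reader might infer that the D132 and D236 comparisons suffer in the same way. Anti-nucleocapsid is scheduled at both visits with a D56 baseline, so seroconverters can be identified there. Larger distortions calculated for infections accumated by D236 do not measure this gap, and a D28 assay would not change them.

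**Conclusion.** The point holds in a limited form. Between D56 and D132 post boost the schedule contains no infection marker, so undiagnosed post-boost infections cannot be flagged at D28, and a seroconversion found at D132 without a dated positive test cannot be placed before or after D28.

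The effect is small if few infections go undetected (0.64 becomes 0.646 at 2%) and moderate at 10% (0.669, with power falling from 90% to 74–81%). These sizes rest on assumed infection shares and fold rises and on a common level after infection; under an equal fold rise with equal shares the GMR is not biased. The primary reactogenicity endpoint is not touched. The change is worth making because it is cheap and because no later analysis can reconstruct the information once the serum is gone.

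**What to change.** 1. In sections 3 and 6 and Appendix C, add anti-nucleocapsid IgG to the serum already drawn at D28 post boost. Amendment 9 in Appendix B is a precedent: troponin and NT-proBNP were added to that sample without extra blood. A negative D28 result in someone seronegative at D56 would also help to clear that person's D14 sample, although it would come too late for the first D14 analysis in section 12.4.
2. Keep the all-samples GMCs and GMRs as planned. Add a supplementary analysis that leaves out samples taken after first evidence of post-boost infection: a positive test, or anti-nucleocapsid seroconversion in those seronegative at D56.
3. Reconcile section 9.6.1.1.5, under which the diary logs SARS-CoV-2 diagnoses over the whole study, with section 13.2, which caps diary reporting of adverse events at 28 days after each vaccine. The D28 visit may fall as late as day 42, so under the cap up to 42 − 28 = 14 days before that visit would rest on the visit check alone.

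Cost: one more assay per participant on existing serum, and one extra analysis. The supplementary analysis conditions on an event after randomisation, which is why it should not replace the all-samples result. It cannot flag reinfection in participants already seropositive at D56, and a D28 test will miss infections too recent to have produced antibody.

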8. PARTICIPANT IDENTIFICATION

8.1. Trial participants

Volunteers aged 12 to 16 years inclusive at enrolment. Comorbidities of clinical definition mild/moderate/well-controlled will be permitted. Individuals of all ethnicities will be recruited, with recruitment of those identifying as Black, Asian and Minority Ethnic particularly encouraged.

8.2. Inclusion criteria

- Parent/legal guardian/Participant is willing and able to give written informed consent for participation in the trial*
- Aged 12 to 16 years inclusive at enrolment
- In good health as determined by a trial clinician. Participants may have well controlled or mild-moderate comorbidity, as long as this would not render them considered as belonging to a ‘high -risk’ cohort at particular need of 2 doses of COVID-19 vaccine (see exclusion criteria below) as part of the national roll out
- Able and willing (in the Investigator’s opinion) to comply with all study requirements

- Registered with a GP, and willing to allow the investigators to discuss the participant's medical history with their General Practitioner and access all medical records when relevant to study procedures.

* Parent/legal guardian to provide informed consent for participants under the age of 16. Participants aged 16 years will be assumed to be able to provide consent for themselves, however parental support will be encouraged and investigators will reserve the right to refuse enrolment if concerns arise.

8.3. Exclusion criteria

The participant may not enter the trial if ANY of the following apply:

- Previous receipt of more than one dose of a COVID-19 vaccine, or a COVID-19 vaccine other than BNT162b2
- Belonging to a 'high risk' cohort advised to receive 2 doses of a COVID-19 vaccine (participants at increased risk of COVID-19, or household contacts of immunocompromised, based on JCVI and 'Green Book' guidelines current on 13th September 2021).
- First degree relative of a study site staff member
- Any confirmed or suspected immunosuppressive or immunodeficient state; asplenia; recurrent severe infections and use of immunosuppressant medication within the past 6 months, except topical steroids or short-term oral steroids (course lasting ≤ 14 days)
- History of anaphylaxis, allergic disease or reactions likely to be exacerbated by any component of study vaccines (e.g. hypersensitivity to the active substance or any of the SmPC/IB-listed ingredients of any study vaccine). This includes latex and polyethylene glycol/macrogol (PEG)
- Pregnancy, lactation or unwillingness to practice effective contraception from enrolment to 3 months post booster vaccination, for post-menarcheal females only
- Malignancy requiring receipt of immunosuppressive chemotherapy or radiotherapy for treatment of solid organ cancer/haematological malignancy within the 6 months prior to consent.
- Bleeding disorder (e.g. factor deficiency, coagulopathy or platelet disorder), or prior history of significant bleeding or bruising following IM injections or venepuncture
- Continuous use of anticoagulants, such as coumarins and related anticoagulants (i.e. warfarin) or novel oral anticoagulants (i.e. apixaban, rivaroxaban, dabigatran and edoxaban)
- Any serious chronic illness requiring hospital specialist supervision
- Congenital cardiovascular conditions

- Severe and/or uncontrolled respiratory disease, gastrointestinal disease, liver disease, renal disease, rheumatological disease, and neurological illness (mild/moderate well controlled comorbidities are allowed)
- History of active or previous auto-immune neurological disorders (e.g. multiple sclerosis, Guillain-Barre syndrome, transverse myelitis)
- Significant renal or hepatic impairment
- Scheduled elective surgery requiring overnight admission and/or general anaesthetic during the trial
- Insufficient level of English language to undertake all study requirements in opinion of the Investigators
- Administration of immunoglobulins and/or any blood products within the three months preceding the planned administration of the vaccines
- Participants who have participated in another research trial involving an investigational product in the past 12 weeks
- Note that a prior history of confirmed or suspected COVID-19 is NOT an exclusion criterion for this study, provided the participant otherwise satisfies the health screening criteria for the study.

8.3.1. Temporary exclusion criteria

If the volunteer has any of the following, they will not be immunised that day.

- Acute respiratory illness (moderate or severe illness with or without fever)
- Fever (oral temperature greater than 37.8°C)
- Receipt of any vaccine (licensed or investigational) within 7 days before enrolment, or intent to receive within 7 days of the COVID-19 vaccines
- Proven COVID-19 infection, first confirmed less than 4 weeks previously (see Section 7.5)

9. TRIAL PROCEDURES

See APPENDIX A: SCHEDULE OF PROCEDURES

9.1. Recruitment

9.1.1. Identification of volunteers

Volunteers will be recruited by methods that may include use of an advertisement +/- registration form formally approved by the ethics committee(s) and distributed or posted by means such as:

- In public places, including buses and trains, with the agreement of the owner / proprietor
- In newspapers or other literature for circulation

- On radio and/or television via announcements
- On a website or social media site operated site or sponsor or with the agreement of the owner or operator (including on-line recruitment through the Oxford Vaccine Group website)
- By e-mail distribution to a group or list only with the express agreement of the network administrator or with equivalent authorisation
- By email distribution to individuals who have already given consent to be contacted for any clinical trial at the Oxford Vaccine Centre and at trial sites including COVID-19 vaccine research
- Direct mail-out using National Health Service databases: These include the National Health Applications and Infrastructure Services (NHAIS) via a NHAIS data extract or equivalent. Initial contact to potential participants will not be made by the study team. Instead, study invitation material will be sent out on our behalf by an external company, CFH Docmail Ltd, in order to preserve the confidentiality of potential participants. CFH Docmail Ltd is accredited as having exceeded standards under the NHS Digital Data Security and Protection Toolkit (ODS ID – 8HN70). Potential participants will be invited to either register their interest directly online using a link to complete our approved ‘Pre Screening Questionnaire’ on the trial website or to return the reply slip in the sealed freepost envelope. Replies will be processed and stored in accordance with local procedures surrounding the handling of identifiable data.
- Oxford Vaccine Centre databases and study site databases: We may contact individuals from databases of groups within the CCVTM (including the Oxford Vaccine Centre database) and other study sites of previous trial participants who have expressed an interest in receiving information about all future studies for which they may be eligible.
- Using local GP practices or Trusts as Participant Identification Centres (PICs)

